For each marketplace condition, participants will complete 10 iterations of the ETM task in ascending order. The prices for menthol cigarettes on the ETM will be set at: \$0.12, \$0.25, \$0.50, \$1.00, \$2.00, \$4.00, \$8.00, and \$16.00 and \$32.00 per cigarette. During one task iteration, menthol cigarettes will be eliminated from the marketplace to simulate a menthol cigarette ban. The costs for the other products will reflect average prices in NC and will not change during the task. For each task iteration, participants will receive individually-tailored account balances approximately equal to the money they would spend on cigarettes for seven days. They can

purchase as many or few products as their account balance allows. Participants are not required to buy products from the ETM or can buy nicotine gum if they prefer to abstain. If they do not buy products from the ETM and do not use tobacco products during the field assessment (biochemically-verified), then they will receive their ETM account balance at Virtual Visit 6. This payment is delayed to reduce the likelihood that they will use this money to buy their preferred brand menthol cigarettes, thus decreasing the validity of the ETM task.

Participants will be instructed to use only the products purchased from the ETM during the subsequent 7-day period after Virtual Visit 5 and told that we will assess adherence by self-report, product accountability, and biochemical verification. The field assessment validates the ETM task by having participants use the products in the real world, simulating the different regulatory environments. Actual product use enables us to measure their subjective experiences such as withdrawal, craving, or product satisfaction as well as assess changes in carbon monoxide exposure, a biomarker of harm, when using products other than menthol cigarettes. We will conduct between-subjects analyses comparing these secondary outcomes by marketplace condition.

In-Person Lab Visit 2

In-Person Lab Visit 2 will be completed up to 48 hours after completing Virtual Visit 5. Participants will complete the COVID screener within 24 hours of their Lab visit via email or phone. Research staff will wear personal protective equipment during the visit including face masks and gloves. The participants will be required to wear facemasks when interacting with the staff. Temperature checks will be conducted immediately upon arrival using a thermal heat scanner.

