Linear mixed-effects models with fixed effects for marketplace condition ('tobacco' vs 'menthol & tobacco' vs 'menthol, mint & tobacco') and order of condition administration, and a random effect for participant (to adjust for correlation induced by repeatedly measuring the same participant) will compare the total amount of non-menthol cigarettes and e-liquids purchased at the highest menthol price (Aims 1 and 2). All products will be converted to mg of nicotine (as listed on their packaging) to standardize purchasing across products, as in previous ETM studies.⁵³⁻⁵⁵ Analyses will be conducted to determine if race moderates product purchasing (Exploratory Aim).

ETM data will be used to generate demand curves for each product using an exponential demand equation. Alpha is the rate of change in demand, Q_0 is peak consumption, C is cost, and k is a constant.

Cross-price elasticity estimates will be calculated as the slope of the regression line (B_1) fit to log-transformed purchasing of each alternative product when offered at fixed prices (C) versus log-transformed menthol cigarette price (P): $\log C = B_0 + B_1 \log P$. Exploratory paired t-tests will compare product purchasing during the pre- and post-field assessment ETM task.

For the qualitative data, we will use grounded theory to develop hypotheses related to the topics of interest. Interviews will be audio-recorded and transcribed verbatim. Audio transcriptions will be reviewed for accuracy and entered into Atlas.ti or another qualitative data management software program. Two research staff members will code the first five interviews to achieve greater than 90% interrater reliability and then every 10th interview to ensure integrity. The research team will analyze the interviews using iterative analyses including qualitative research techniques of open and axial coding; major thematic categories; analytical domains; triangulation of data; comparisons within and between groups; and documenting analytical pathways. Saturation will be achieved when no new themes emerge.

HUMAN SUBJECTS PROTECTION

Recruitment Methods

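### Three secondary or supportive marketplace analyses cannot be run as written: demand curves for fixed-price products, the condition model for mint and fruit/dessert e-liquid, and log-log elasticity at zero purchases

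*Combined protocol and SAP*

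**What the plan says.** All references are to the combined protocol and SAP.

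- **Demand curves (Statistical analysis plan).** "ETM data will be used to generate demand curves for each product using an exponential demand equation". The terms are defined as "Alpha is the rate of change in demand, Q_0 is peak consumption, C is cost, and k is a constant".
- **Prices (Virtual Visits 2-5).** Menthol cigarettes have nine listed prices, from $0.12 to $32.00 each. For everything else: "The costs for the other products will reflect average prices in NC and will not change during the task". A tenth iteration has no menthol price: "During one task iteration, menthol cigarettes will be eliminated from the marketplace to simulate a menthol cigarette ban".
- **Condition model (Statistical analysis plan).** "Linear mixed-effects models with fixed effects for marketplace condition ('tobacco' vs 'menthol & tobacco' vs 'menthol, mint & tobacco" and so on, labelled for Aims 1 and 2. It compares purchases of non-menthol cigarettes and e-liquids at the highest menthol price.
- **Markets (Virtual Visits 2-5).** Condition 1 sells tobacco e-liquid, Condition 2 adds menthol, Condition 3 adds mint, and Condition 4 adds fruit and dessert.
- **Outcomes (Analysis Plan).** The secondary outcomes are purchases of tobacco, menthol, mint and dessert/fruit e-liquid when menthol cigarettes are unavailable. The same purchases by race are exploratory.
- **Elasticity (Statistical analysis plan).** Log purchasing of each alternative product is regressed on log menthol cigarette price. Participants may buy nothing: "Participants are not required to buy products from the ETM".

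**The concern.** A demand curve in own cost needs that cost to vary, and for nine products it does not. A condition model can analyse a flavour only in markets that sell it. For fruit/dessert there is no such market in the model, and for mint there is one, so its purchases would be set against zeros that the design imposes. A logarithm of purchasing is undefined at zero.

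At stake are the secondary e-liquid outcomes and the supportive demand analyses. A listed secondary outcome without a workable stated analysis leaves the method to be chosen after the data are seen. A literal run would give arbitrary demand parameters, a mint comparison with a wrong standard error, and elasticities that depend on an undeclared choice.

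**Working it through.** **Power figures first.** The plan claims 80% power with 80 participants for both aims. For Aim 1, a paired t-test at d = 0.31 (two-sided 0.05 assumed) gives 78.2% by the noncentral t and 79.2% by the normal approximation. For Aim 2, two one-sided tests at 0.05 with a margin of 0.33 SD and a true difference of zero give 80.0% (t, simulated) or 80.9% (normal). Both reproduce the plan closely, and nothing below changes them.

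**1. Demand curves**

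*Inputs.* The Virtual Visits 2-5 section lists ten products: two cigarettes, five e-liquids and three gums. One of them has nine prices and nine have one price each. The equation is not in the extracted text, so the standard exponential form is assumed: log10 Q = log10 Q0 + k(exp(−α·Q0·C) − 1).

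*Identifiability.* At a single price with Q = 20 mg, solving for α gives α = −ln(1 + log10(20/Q0)/k)/(Q0·C). Take k = 2 and C = 1 for illustration:

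- Q0 = 25 gives α = 0.0019867, and the curve returns 20.00 mg.
- Q0 = 200 gives α = 0.0034657, and the curve again returns 20.00 mg.

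Any Q0 between 20 and 2,000 fits exactly with its own α. The Jacobian in (Q0, α) has rank 2 over the nine menthol prices and rank 1 at one fixed price.

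*Reading C as the menthol price instead.* Suppose a substitute's purchases rise as 20·P^0.5, which is 6.9 to 113 mg over the nine prices. The best fit with k = 2 is α = −0.0007, Q0 = 17.7, R² = 0.64. The rate is negative, and Q0 is far below the largest purchase, so it is not peak consumption as the plan defines it.

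**2. Condition model**

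*Inputs.* 80 completers, and the flavours sold in each market. The number of selling markets is the same at the ban iteration, which defines the outcomes, and at the highest menthol price, which the model names.

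| E-liquid | Sold in | Selling-market observations in the model | Contrasts between two selling markets in the model |
|---|---|---|---|
| Tobacco | 1-4 | 3 × 80 = 240 | 3 |
| Menthol | 2-4 | 2 × 80 = 160 | 1 |
| Mint | 3-4 | 1 × 80 = 80 | 0 |
| Fruit/dessert | 4 | 0 | 0 |

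*Mint, run literally.* Each participant contributes (0, 0, Y). Let s² be the variance of Y and n = 80, and leave aside the order term.

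- The Condition 3 minus Condition 1 difference is the mean of Y, whose true standard error is s/√n.
- After removing participant and condition means, a participant with deviation e = Y − mean(Y) has residuals −e/3, −e/3 and 2e/3. Their squares sum to (1/9 + 1/9 + 4/9)e² = (2/3)e².
- The residual mean square is (2/3)(n − 1)s² / [2(n − 1)] = s²/3.
- The participant mean square is 3(n − 1)(s²/9)/(n − 1) = s²/3. The two are equal, so the random-effect variance is estimated as zero.
- The model's standard error is √(2 · s²/3 / n) = √(2/3) · s/√n = 0.816 · s/√n, which is about 18% too small.

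Fitting such data by restricted maximum likelihood gave the same ratio, 0.816.

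*What selling-market analyses can deliver.* A 95% interval for fruit/dessert in Condition 4 has half-width 1.990/√80 = 0.22 SD overall and 2.023/√40 = 0.32 SD per race group (40 each). A paired comparison of mint in Condition 3 vs 4 with n = 80 detects d = 0.317 with 80% power.

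**3. Elasticity at zero**

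The plan gives neither a zero rule nor a level of fit (individual or group). Take one invented buyer with purchases of 0, 0, 0, 0, 20, 40, 60, 80, 80 mg over the nine prices. The slope is 0.50 with zeros dropped, 1.02 after adding 1, 1.57 after adding 0.1 and 2.12 after adding 0.01. With zeros dropped, a participant who never buys has no slope. With a constant added, that participant's slope is 0.

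In simulations with assumed zero rates of 9% to 46%, a true slope of 0.50 and no purchase cap, individual fits gave 0.28 to 0.45 dropping zeros, 0.55 to 0.84 adding 0.01, and 0.23 to 0.40 adding 1 unit. Adding 1 mg after an assumed 50 mg per unit gave 0.52 to 0.76. The unit therefore matters too, since "All products will be converted to mg of nicotine (as listed on their packaging) to standardize purchasing across products". These runs show a mechanism and do not estimate this trial's bias.

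**The case against.** - **Three levels are deliberate.** This stands. The model is labelled for Aims 1 and 2, and both aims concern Conditions 1 to 3. A reader might infer that leaving out Condition 4 is an error in the aims' analysis, or that tobacco and menthol e-liquid lose data they need. The documents do not support that: those outcomes keep valid contrasts in the model.
- **No between-market comparison of mint is promised.** This also stands. The outcome list names amounts purchased. It would be too strong to say that a planned mint contrast is missing. The defect is that the only stated model would make an invalid one.
- **Fruit/dessert can only be described.** True, since one market sells it, but the plan does not say so. The between-subjects comparisons under Virtual Visits 2-5 concern field-assessment outcomes such as withdrawal and carbon monoxide. The sentence on race as a moderator names neither a model nor conditions.
- **The intent for demand curves is plain.** Probably. The next analysis in the plan recognises that alternatives have fixed prices and gives them a cross-price elasticity. The instruction covering every product still cannot be followed.
- **The elasticity problem is unquantified.** Correct, because the zero rate is unknown. In some simulated settings with capped purchases, dropping zeros did about as well as the alternatives. A reader might also infer that the ban iteration corrupts the regression. Having no price, it drops out of a regression on log price by itself.

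**Conclusion.** The point holds for secondary and supportive analyses only. A reader might infer that the main comparisons are compromised. They are not: the primary outcome, sample size and stated power are untouched.

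- **Demand curves:** not estimable in own price for nine of ten products. This follows from the fixed prices. Only the numerical illustration depends on the assumed equation.
- **Condition model:** this is the part that bears on listed outcomes. Fruit/dessert has none of its 80 observations in the model. Mint, run literally, is tested against design zeros with a standard error about 18% too small. The 18% assumes a common residual variance, a participant random intercept, complete data and no order effect. If e-liquids in the model means an all-flavour total, none of the flavour-specific secondary outcomes has a stated model.
- **Elasticity:** minor. The dependence on the zero rule is real and can be large, but its size here is unknown. The simulations do not establish one best method, because the target used under a purchase cap, the slope of mean purchases, favours group means.

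**What to change.** 1. Limit demand curves to menthol cigarettes, and describe the alternatives by the cross-price elasticity already planned.
2. Keep the three-level model for non-menthol cigarettes and tobacco e-liquid. For each other flavour use only markets that sell it, at the menthol-ban iteration that defines the outcomes:
   - menthol e-liquid: Conditions 2 to 4, or 2 vs 3;
   - mint: summarised in Conditions 3 and 4, with a 3 vs 4 comparison optional;
   - fruit/dessert: summarised with a confidence interval in Condition 4, overall and by race.

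   State whether e-liquids in the Aim 1 and 2 model means an all-flavour total.
3. Fit the elasticity to group mean purchases over the nine priced iterations with participant-level bootstrap intervals, or use a log-link quasi-Poisson model with participant-clustered errors. Report individual log-log slopes, with a stated zero rule and unit, as a sensitivity analysis.

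**Cost.** SAP wording and small code changes, with no new data and no change in sample size. Elasticities become slightly less comparable with earlier log-log estimates, which the sensitivity analysis addresses, and group means give no individual elasticities. Neither elasticity method removes the effect of the account-balance limit on purchases.

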Participants will provide CO readings be at least 6-feet away from other people, including the research staff, while they have their masks off.

Participants will be given the products they purchased during the ETM task and will be instructed to only use these products for the next seven days. They will also be given a urine collection cup and instructions for sample collection.

Virtual Visit 6

Participants will complete Virtual Session 6 seven days after completing In-Person Lab Visit 2. They will bring a first morning void urine sample, which will be banked for future biomarker analysis (e.g., total nicotine equivalents).

The following baseline assessments will be administered as an interview and entered into REDCap by the interviewer:

1. Timeline Follow Back (TLFB) Questionnaire which will assess past tobacco and nicotine product use since Virtual Visit 5.

The following surveys will be self-administered using REDCap:

1. Tobacco Policy Questionnaire
2. Minnesota Nicotine Withdrawal Scale

3. Questionnaire of Smoking Urges-Brief – Usual Brand Cigarette
4. Product Evaluation Scale
5. Perceived Health Risks Scale
6. Tobacco Product Interest Scale

Participants will complete the ETM task under the same marketplace condition from which they received their field assessment products. Exploratory pre-post field assessment analyses will examine how actual use of the products affects subsequent purchasing of those products.

Research staff will conduct in-depth interviews with the participants to assess the following constructions: 1) decision-making during the ETM task; 2) use of alternative products during the field assessment; 3) product risk perceptions and; 4) opinions regarding possible tobacco control policies.

In-Person Lab Visit 3

In-Person Lab Visit 3 will be completed up to 48 hours after completing Virtual Visit 6. Participants will complete the COVID screener within 24 hours of their Lab visit via email or phone. Research staff will wear personal protective equipment during the visit including face masks and gloves. The participants will be required to wear facemasks when interacting with the staff. Temperature checks will be conducted immediately upon arrival using a thermal heat scanner. Participants will bring a first void urine sample and all of their used/unused products.

Participants will provide CO readings at least 6-feet away from other people, including the research staff, while they have their masks off.

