10. **Smoking and Oral Contraceptives in Women:** Women who smoke and are over the age of 35 should not take oral contraceptives that contain estrogen without consulting their

physician. Smoking while using oral contraceptives can increase the risk of having a cardiovascular event such as a heart attack or stroke. Additionally, there is a potential risk of thrombosis associated with hormonal therapy (including contraceptives) and smoking.

Avoiding Risks during Pregnancy

Smoking during pregnancy can lead to miscarriage, preterm delivery, stillbirth, birth defects, and other problems. To avoid risks to the participant and fetus, female participants will be tested for pregnancy at the Screening Visit.

Expected benefits of participation

There are no immediate benefits from participating in the study. The information obtained from this study may ultimately help the Food and Drug Administration (FDA) decide how best to regulate tobacco products with the goal of improving public health.

Reporting Unanticipated Problems, Adverse Events or Deviations

Identifying Adverse Events

While participating in the study, adverse events will be assessed at Virtual Visit 6 and carbon monoxide levels from In-Person Lab Visit 3. Adverse events will typically be identified during the administration of the Health Changes Questionnaire. Other adverse events may be identified by spontaneous reports from the participant. Withdrawal symptoms are considered an adverse event if the symptom had a significant impact on the participant's daily life, caused a major disruption of functioning, or took any medication for it.

- Health Changes Questionnaire: If the participant answers "YES" to Questions 1, 2, or 3 the interviewer should assess for adverse events.
 1. Have you had any negative changes in your physical or mental health since your last virtual visit? If yes, briefly describe.
 2. Since your last virtual visit, have you received any form of medical care? If yes, briefly describe.
 3. Have you had any changes in medication since your last visit?

Physiological data that will be reviewed:

1. CO level: The 'Adverse Event Form' will be completed if the average of two (or three) consecutive measurements in the same visit is:
 - o CO is greater than 50 ppm if CO at Screening/Baseline Visit is < 20 ppm.
 - o CO is greater than 60 ppm if CO at Screening/Baseline Visit is 20 – 34 ppm.
 - o CO is greater than 70 ppm if CO at Screening/Baseline Visit is 35 – 49 ppm.

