For the participant's protection, participants will be withdrawn immediately from the study if any of the following occur:

1. Cardiovascular disease (CVD) event: Typically includes MI (heart attack), PTCA (angioplasty/stenting), bypass surgery, stroke, peripheral vascular disease (arterial

blockages in arms or legs leading to procedure or surgery). Less common CVD problems would be new cardiac arrhythmias (e.g., new atrial fibrillation) or new valvular disease (e.g., mitral or aortic regurgitation).

2. DVT/PE (deep vein thrombosis/pulmonary embolism, i.e., blood clots in the venous system).
3. Suicide Attempt: A participant will be withdrawn if they attempt suicide at any time during participation in the study
4. Psychiatric Hospitalization: A participant will be withdrawn if they are hospitalized for psychiatric reasons at any time during participation in the study.
5. Pregnancy: If a participant indicates they are pregnant at Virtual Visit 6 or In-Person Lab Visit 3, they will be withdrawn from the study, and this event will remain open until delivery. At that time the license medical monitor will contact the participant to ask a few questions about the baby's health and will update the open 'Adverse Event Form'.

The following will be monitored and can lead to the participant being withdrawn by the PI or Licensed Medical Monitor:

1. Expired breath CO >80 ppm
2. Any hospitalization or debilitation in which participation in the study could be detrimental to the recovery process. This will be self-reported by the participant and will be reviewed by the site PI and medical monitor to determine whether continued participation in the study is appropriate.
3. If a participant is behaving in an inappropriate or threatening manner, admits to lying about eligibility criteria, including omitting previous medical diagnoses and medications, is participating in other smoking research studies that could affect the primary outcome measures, does not follow study instructions, etc., then the PI can withdraw them from the study at the PI's discretion.
4. If a participant fails to attend her/his Virtual Visit 1 within the 21-day allowable visit window, they will not be eligible to reschedule the visit or continue participation in the study.

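### As written, no health-change or pregnancy question is scheduled between In-Person Lab Visit 1 and dispensing of a week of products at In-Person Lab Visit 2

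*Combined protocol and SAP*

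**What the plan says.** **Timing of adverse-event assessment.** The section Identifying Adverse Events states that "adverse events will be assessed at Virtual Visit 6 and carbon monoxide levels from In-Person Lab Visit 3". Events are typically to be found with the three-question Health Changes Questionnaire; spontaneous reports are a further route. Question 1 asks "Have you had any negative changes in your physical or mental health since your last virtual visit", and question 2, on medical care, has the same look-back. Question 3 is worded differently: "Have you had any changes in medication since your last visit".

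**Withdrawal rules.** For protection, "participants will be withdrawn immediately from the study if any of the following occur": a cardiovascular event, DVT/PE, suicide attempt, psychiatric hospitalization or pregnancy. The suicide and psychiatric items apply throughout participation. The pregnancy item is tied to two visits: "If a participant indicates they are pregnant at Virtual Visit 6 or In-Person Lab Visit 3, they will be withdrawn from the study". A second list allows discretionary withdrawal, including for a self-reported hospitalization or debilitation, which the PI and medical monitor review. That rule is not tied to a visit.

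**Before dispensing.** In-Person Lab Visit 1 includes the urine pregnancy test and product sampling. Virtual Visits 2-5 list the tobacco-use interview, the Minnesota Nicotine Withdrawal Scale, the smoking-urges questionnaire and the purchasing task. For In-Person Lab Visit 2, "Participants will complete the COVID screener within 24 hours of their Lab visit via email or phone"; temperature is checked on arrival; "Participants will provide CO readings be at least 6-feet away from other people"; and then "Participants will be given the products they purchased during the ETM task", for seven days of use.

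**The concern.** The protocol has mandatory withdrawal rules, and the natural moment to apply them is just before products are handed over. Yet its only stated adverse-event assessment comes after the week of use. A participant who has had a qualifying event since Lab Visit 1 could be given products before anyone asks. The later questionnaire, with its short look-back, would not recover the event either. The same applies to a reaction to the products sampled at Lab Visit 1.

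Dispensing changes exposure. Participants are told to use only what they bought, and the products come from the task iteration without menthol cigarettes. The protocol's own risk section warns that changes in nicotine use can worsen mood and psychiatric symptoms. What is at stake is participant protection, not the estimates or tests.

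**Working it through.** The protocol gives no figure to reproduce. The check sets the visit contents against the safety rules and adds up the visit windows.

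**Step 1. What is asked between Lab Visit 1 and dispensing.**

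- *Virtual Visits 2-5:* product use, withdrawal symptoms and smoking urges. The protocol counts disruptive withdrawal symptoms as adverse events, but no rule links scores on the withdrawal scale to an adverse-event review.
- *Lab Visit 2:* COVID screener, temperature and CO. The screener's items are not given. The nearest text, exclusion criterion 4, names fever, cough and runny nose.
- No listed item asks about new illness, medical care, medication or pregnancy.

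**Step 2. Visit windows (from the visit descriptions).**

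- Lab Visit 1 to Virtual Visit 2: 1 to 21 days.
- Virtual Visits 2 to 5: 3 days if consecutive. The limit of 7 days apart gives at most 7 days if it spans the block, or 3 × 7 = 21 days if it applies to each of the three gaps.
- Virtual Visit 5 to Lab Visit 2: 0 to 2 days.
- Lab Visit 2 to Virtual Visit 6: 7 days.

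**Step 3. Sums, in days.**

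| Interval | Ideal schedule | Maximum, block reading | Maximum, per-gap reading |
|---|---|---|---|
| Lab Visit 1 to Virtual Visit 5 | 1+3 = 4 to 21+3 = 24 | 21+7 = 28 | 21+21 = 42 |
| Lab Visit 1 to dispensing at Lab Visit 2 | 4+0 = 4 to 24+2 = 26 | 28+2 = 30 | 42+2 = 44 |
| Lab Visit 1 to Virtual Visit 6 | 4+7 = 11 to 26+7 = 33 | 30+7 = 37 | 44+7 = 51 |

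The maxima need every window at its limit.

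**Step 4. How far back the Virtual Visit 6 questions reach.** Questions 1 and 2 go back to Virtual Visit 5: (0 to 2) + 7 = 7 to 9 days. Question 3 reaches 7 days if the last visit means Lab Visit 2. The first row of the table is therefore covered by no health-change question, even in retrospect. Moving questions 1 and 2 unchanged to Lab Visit 2 would not help, because there they would reach back only 0 to 2 days.

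**Step 5. Rules against contacts.** Five contacts run from Virtual Visit 2 to Lab Visit 2 inclusive. The cardiovascular, DVT/PE, suicide, psychiatric and hospitalization rules can act at any of them, but only if the participant volunteers the event. The pregnancy rule names none of the five. Its first named visit is 11 to 33 days after the pregnancy test on the ideal schedule.

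**The case against.** **Absence from the visit lists proves little.** The Health Changes Questionnaire is in no visit's list, not even that of Virtual Visit 6, where the protocol intends adverse-event assessment. Its look-back to the last virtual visit would also suit repeated use. This stands: a reader might infer that participants are definitely not asked earlier, and the documents do not show that. The point rests instead on the stated timing, which names Virtual Visit 6 alone.

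**Events before dispensing are already covered by rule.** This also stands. A reader might infer that the protocol has no provision for them. It does: two of the mandatory rules run throughout participation, and the hospitalization rule is not tied to a visit. What is missing is a scheduled prompt to bring the event to light.

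**The pregnancy item is being read strictly.** It sits under a heading requiring immediate withdrawal on occurrence, and pregnancy is an exclusion criterion. It would be too strong to say that the protocol lets a known pregnant participant continue; staff would hardly be without direction. The wording still ties the rule to two visits, both after field use.

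**The timing is defensible.** Study exposure before Lab Visit 2 is brief: up to two minutes per product. History, medications and a pregnancy test come before it, and staff have contact at every visit. This explains why the main assessment follows the field week. It is not a reason to omit a check before that week begins.

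**The added risk is small.** Accepted. Participants already smoke at least 5 cigarettes a day and continue until dispensing. Serious medical and psychiatric conditions are excluded, as are intended pregnancy and refusal of adequate protection. Withholding products would not by itself end tobacco exposure, and a question would not find an unrecognised pregnancy.

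**Conclusion.** The point holds as a minor one. Followed as written, the protocol schedules no health-change or pregnancy question in the 4 to 26 days (ideal schedule; at most 30 or 44) before a week of products is dispensed, so its withdrawal rules then rely on unprompted report.

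This rests on two assumptions: that the COVID screener and the withdrawal scale do not ask about medical care, cardiovascular or psychiatric events, or pregnancy; and that the questionnaire is not used before Virtual Visit 6. The documents give neither the items nor any earlier use. If staff already ask earlier, a sentence saying so, with the look-back stated, would settle most of the point.

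A reader might infer a serious safety failure or a threat to the results. The documents support neither. They give no event rate from which to estimate how many participants would be affected, the added risk is probably small, and the trial's conclusions are unaffected.

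**What to change.** 1. At In-Person Lab Visit 2, before hand-over, give the existing three-question Health Changes Questionnaire with all three items worded as *since Virtual Visit 1*. Medical history and medications were recorded then, so this wording also covers the time between Virtual Visit 1 and Lab Visit 1.
2. Add one pregnancy question for participants with child-bearing potential.
3. Assess any positive answer by the existing adverse-event procedure before dispensing. Allow dispensing to go beyond 48 hours after Virtual Visit 5 if the medical monitor must review it.
4. Extend the pregnancy withdrawal rule to a pregnancy reported at any visit.

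Nothing is added at Virtual Visits 2-5, and the other withdrawal rules stay as they are.

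**Cost.** At most 3 + 1 = 4 short items per participant at a contact already held: 4 × 80 = 320 answers for 80 completers, or 4 × 100 = 400 if all 100 recruits reach Lab Visit 2. The downsides are a slightly longer Lab Visit 2, a few more recorded events and occasional delayed dispensing.
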